10.3. Hypotheses

10.3.1. Primary Hypothesis

These studies are intended to assess whether there is a difference between patients treated with OCA and comparable OCA-eligible patients who are not treated with OCA in the time from index to the first occurrence of all-cause death, liver transplant, or hospitalization for hepatic decompensation.

Two-sided hypotheses are expressed in terms of:

- The null hypotheses (H₀) that the 2 hazard functions are the same, as determined by a hazard ratio (HR) equal to 1; that is, at every timepoint, the instantaneous event rates are the same for the OCA and control populations.
- The alternative hypothesis (H₁) that the 2 hazard rates are not the same ($HR \neq 1$).

10.4. Determination of Sample Size

Using the sample size in the 2 populations (Section 6.2), the Sponsor computed power to detect treatment effects (relative hazards) of varying sizes, estimated using Cox proportional hazards regression. Computations are based on the formulae of Schoenfeld 1983. To account for confounding control due to the application of IP weights, the Sponsor inflated the variance from the Schoenfeld formula using factors derived by Shook-Sa 2020. It was conservatively assumed just one control observation per patient. In the Komodo Health data, a preliminary investigation found that approximately 395 patients who meet entry criteria will initiate OCA and that 5916 patients will contribute at least one record to the control group (UDCA nonresponders). In the Global PBC registry, the Sponsor expects to have 344 patients meeting entry criteria who initiate OCA, and 2200 who contribute at least one observation to the control group. Power in both cohorts was computed for relative hazards ranging from 0.5 to 0.9 with an alpha level of 0.05. The Sponsor considered baseline event rates during follow-up from 5% to 15% and variance inflation corresponding to mild confounding (VIF=1.05), moderate confounding (VIF=1.5), and strong confounding (VIF=2.0). In each study, power was plotted under these assumptions against a reference line of 80% power under moderate confounding (VIF=1.5) (Figure 2).

Under mild confounding, both studies will be well-powered to detect an HR of 0.5. For moderate confounding, the Komodo Health study will be adequately powered to detect HR of 0.5 for event rates >6%. The Global PBC registry will be adequately powered to detect event rates >8%. Under strong confounding, the Komodo Health study will be adequately powered to detect

HR of 0.5 for event rates >9%. The Global PBC registry will be adequately powered to detect event rates >11%. Power decreases for more moderate HRs. None of the studies under even the most favorable assumptions will be able to detect HRs of 0.9. The Sponsor notes that the assumptions made here are conservative; in particular, it is expected that many more than one control observation and that the addition of lab data from LabCorp (as noted in Section 6.2) will substantially increase the size of both groups in the Komodo Health study.

Figure 2: Power estimates by Hazard Ratio by Level of Confounding for Komodo Health (A) and Global PBC Registry (B).

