After the index date, follow-up will continue until the first of the composite outcome event (all-cause death, liver transplant, or hepatic decompensation), censoring, treatment discontinuation (for patient indices initiating OCA on the index date), OCA initiation (for patient indices not initiating OCA on the index date), or the end of the study period.

Because treatment will not be randomized, it is likely that OCA-treated and non–OCA-treated patient indices will differ on confounding variables, ie, variables that influence both treatment and outcome. Therefore, a simple comparison of outcomes among the OCA-treated versus non–OCA-treated patient indices is likely to yield a biased estimate of the effect of OCA on the study endpoint. To address differences in the covariate distribution between groups, the Sponsor will first conduct descriptive analyses on all baseline variables (demographics, clinical characteristics, and treatment history) for the OCA-treated and non–OCA-treated groups at index. Means, standard deviations, medians, inter-quartile ranges, and minimums and maximums will be provided for continuous variables. Counts and percentages will be provided for categorical variables. Appropriate tests comparing cohorts of interest in the primary and exploratory analyses (eg, t--test, chi-squared test) will be used based on the distribution of the measure.

Next, standardized mortality/morbidity ratio weights will be used to create a "pseudo-population" of non–OCA-treated indices with the same covariate distribution as the OCA-treated patients at the time of OCA initiation (Sato 2003), and unweighted and weighted standardized mean differences (SMDs) will be computed. SMR weights result in an average effect of treatment among the treated. They often make more efficient use of data in a situation with a small treatment group compared with inverse-probability of treatment weights. The SMR weights will be estimated as:

 $w_i^t = \frac{\hat{\pi}_i(1)}{\hat{\pi}_i(A_i)}$, where w_i^t is the weight for patient index *i*, A_i is the observed level of treatment for patient index *i* (A = 1 if the patient index is OCA-treated, 0 otherwise), X_i is the vector of confounders measured at the index time for patient index *i*, and $\pi_i(a) = \Pr(A = a | X_i)$ is the probability that patient index *i* receives treatment level *a* conditional on their covariates.

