10.5. Primary Efficacy Analysis

Standard error estimation will proceed using the nonparametric cluster bootstrap (Davison 2013) as has been suggested for nested trial designs using Cox proportional hazards regression (Gran 2010). The standard error will be used to calculate the 95% CI of the hazard ratio and to conduct statistical hypothesis testing. A total of 1000 bootstrap replicates will be used. Bootstrap sampling will occur at the patient level, rather than the patient index level, thus preserving the covariance structure between patient indices and properly accounting for variance inflation due to the covariance between analytic units. Within each bootstrap replicate, all aspects of estimation will be repeated, including the fitting of the treatment model, the construction of the weights, and the fitting of the weighted Cox proportional hazards model used to estimate the treatment effect. The standard deviation of the bootstrap estimates of the treatment effect will be used as an estimate of the standard error. A Wald test will then be conducted using the bootstrap standard error (Cameron 2008). The test statistic is defined as

 $w = \frac{\hat{\beta}}{s_{\hat{\beta}}}$, where $\hat{\beta}$ is the estimated coefficient of OCA treatment from the fitted Cox model and $s_{\hat{\beta}}$ is the bootstrap standard error of the estimated coefficient. With a sufficient sample size, w will follow a standard normal distribution and the p-value will be computed as the probability of a normal random variable being greater than |w| or less than -|w|. A p-value less than 0.05 will be considered statistically significant.

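### Section 10.4 and the synopsis overstate power for a hazard ratio of 0.5 under mild and moderate confounding, in part even by the plan's own formula

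*Combined protocol and SAP*

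**What the plan says.** Section 10.4 computes power by Schoenfeld's formula for 395 OCA and 5916 control patients (Komodo) and 344 and 2200 (registry), with one control record per patient. To allow for weighting, "the Sponsor inflated the variance from the Schoenfeld formula" by 1.05 (mild confounding), 1.5 (moderate) or 2.0 (strong). On the event rate it says: "The Sponsor considered baseline event rates during follow-up from 5% to 15" percent. It does not say whether that is the rate in controls, in OCA patients or overall.

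The conclusions for a hazard ratio (HR) of 0.5 are:

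- Mild: "Under mild confounding, both studies will be well-powered to detect an HR of 0.5", with no event-rate limit.
- Moderate, Komodo: "For moderate confounding, the Komodo Health study will be adequately powered to detect HR of 0.5 for event rates >6" percent.
- Moderate, registry: "The Global PBC registry will be adequately powered to detect event rates >8" percent.
- Strong: above 9% (Komodo) and above 11% (registry).

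It adds: "The Sponsor notes that the assumptions made here are conservative", citing additional control records and the LabCorp linkage. The synopsis (Sample Size Justification) repeats all of this.

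The planned test is a Wald test with a patient-level bootstrap standard error (Section 10.5): "Within each bootstrap replicate, all aspects of estimation will be repeated, including the fitting of the treatment model, the construction of the weights". On the weights, Section 10.1.1 says: "SMR weights result in an average effect of treatment among the treated".

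**The concern.** There are two separate problems. First, some of the statements do not follow from the disclosed formula at the event rates to which they are applied. Second, Schoenfeld's variance is evaluated at HR 1. With OCA patients making up only 6% to 14% of each cohort, that credits the OCA group with about twice the events it would have at HR 0.5, and those few events dominate the variance of the log hazard ratio.

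The cohorts already exist and the 95% CI will show the precision achieved, so no enrolment decision depends on this. What is at stake is how the plan's power claims, and a non-significant result, would be read.

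**Working it through.** **Inputs.** Group sizes, VIFs, HR 0.5, alpha 0.05, the 80% reference line and the 5% to 15% range come from Section 10.4. The two-sided test comes from Section 10.3.1, so z = 1.96. Let r be the quoted event rate, n1 and n0 the OCA and control numbers, and p = n1/(n1 + n0). Komodo: p = 395/6311 = 0.0626, p(1−p) = 0.05867. Registry: p = 344/2544 = 0.1352, p(1−p) = 0.11694.

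**Step 1: the plan's own method.** Power = Φ(ln 2 · √(D·p(1−p)/VIF) − 1.96). Total events D are (n1 + n0)·r if r is the overall rate, or n0·r + n1·(1 − (1−r)^0.5) if r is the control rate.

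- Komodo, 6%, VIF 1.5, overall rate: D = 378.7; 0.6931 × √(378.7 × 0.05867/1.5) = 2.668; Φ(0.708) = 76%.
- Registry, 5%, VIF 1.05, overall rate: D = 127.2; 0.6931 × √(127.2 × 0.11694/1.05) = 2.609; Φ(0.649) = 74%.

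| Scenario | Plan's statement | Power at that rate (overall / control reading) | 80% reached at |
|---|---|---|---|
| Komodo, VIF 1.05, 5% | no limit | 83% / 82% | 4.6% / 4.8% |
| Registry, VIF 1.05, 5% | no limit | 74% / 71% | 5.8% / 6.2% |
| Komodo, VIF 1.5, 6% | >6% | 76% / 75% | 6.6% / 6.8% |
| Registry, VIF 1.5, 8% | >8% | 79% / 76% | 8.2% / 8.8% |
| Komodo, VIF 2.0, 9% | >9% | 81% / 80% | 8.8% / 9.1% |
| Registry, VIF 2.0, 11% | >11% | 80% / 77% | 11.0% / 11.8% |

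The overall-rate reading reproduces the strong-confounding thresholds. By the same method, the mild statement fails for the registry at the low end, and the Komodo figure of 6% is somewhat low.

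**Step 2: OCA events.** The null variance credits the OCA group with n1·r events: 395 × 0.06 = 23.7 (Komodo) and 344 × 0.08 = 27.5 (registry). If r is the control rate, HR 0.5 gives 395 × (1 − √0.94) = 12.0 and 344 × (1 − √0.92) = 14.0. At 5% the figures are 10.0 and 8.7.

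**Step 3: no confounding at all.** An unweighted Cox Wald test was simulated with r as the control rate, equal follow-up, one record per patient and VIF 1. Power is about 71% (Komodo, 6%) and 77% (registry, 8%). Schoenfeld on the same reading gives 90% for both: D = 367.0 and 190.0, so Φ(3.216 − 1.96) and Φ(3.268 − 1.96). At 5% the simulated power is about 61% and 53% (51% for the registry in a second run). On this reading the mild statement also fails for Komodo at the low end.

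**Step 4: adding VIF 1.5.** The weight is π(1)/π(A), which is 1 for every OCA record, so the weights vary only among controls. A matching approximation is power = Φ(ln 2/√(1/d_OCA + VIF/d_control) − 1.96).

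- Komodo, 6%: 1/12.03 + 1.5/355.0 = 0.0873; SE 0.2955; Φ(0.386) = 65%.
- Registry, 8%: 1/14.05 + 1.5/176.0 = 0.0797; SE 0.2823; Φ(0.495) = 69%.

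This form is somewhat pessimistic: at VIF 1 it gives 66% and 71%, against the simulated 71% and 77%.

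**Step 5: sensitivity to the undefined rate (6% / 8%, VIF 1.5, same form).** Overall rate: 66% / 72%. OCA-arm rate: OCA events 23.7 and 27.5, control events 5916 × (1 − 0.94²) = 688.6 and 2200 × (1 − 0.92²) = 337.9, giving 91% / 93%.

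**Step 6: extra controls and LabCorp.** With unlimited controls only 1/d_OCA remains: Φ(0.6931 × √12.03 − 1.96) = 67% (Komodo, 6%) and Φ(0.6931 × √14.05 − 1.96) = 74% (registry, 8%). Doubling both Komodo groups (790 and 11832) at 6% and VIF 1.5 gives 1/24.07 + 1.5/709.9 = 0.0437 and power of 91%.

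**The case against.** The strongest defence is that the moderate and strong thresholds are close to what the disclosed formula yields. If above 6% and above 8% mean the next whole percent, Schoenfeld gives 82% / 81% at 7% (Komodo) and 83% / 81% at 9% (registry) on the overall / control readings. That is a fair answer to the first problem for the moderate thresholds. It does not answer the unlimited mild statement for the registry. Nor does it address the second problem: the closed form gives 72% at 7% and 74% at 9%.

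A second defence is that the 'conservative' remark cites LabCorp enlarging both Komodo groups, and Section 6.2 expects approximate doubling. That would add OCA events and largely restore Komodo's power. It does nothing for the registry, and it is not in the stated figures. The other reason cited, more control records per patient, does not add OCA events.

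Three stronger readings are tempting but not supported.

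- A reader might take 8.5% and 10.4%, where the closed form reaches 80% at VIF 1.5, as the correct thresholds. They assume a control-arm rate and a VIF on the controls only, neither of which Section 10.4 states, and the closed form is pessimistic.
- A reader might inflate the whole event-based variance, as the text literally suggests, and conclude that the 9% and 11% thresholds fail too (54% and 55%). That does not match SMR weights. With inflation on the controls, those thresholds give 82% and 81%.
- A reader might conclude that the studies need more patients. These are existing cohorts, and the point concerns only how power is described.

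Figure 2 is not visible here, so any limits shown on its curves could not be checked.

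**Conclusion.** The power statements for HR 0.5 under mild and moderate confounding are too favourable as written.

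The firmest part needs only the plan's own method, with the rate read as overall or control. The registry under mild confounding falls 6 to 9 points short of 80% at the 5% event rate, and Komodo at 6% under moderate confounding falls 4 to 5 points short.

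The second part rests on reading the quoted rate as the control rate. About 12 and 14 OCA events then hold power to about 71% and 77% with no confounding, and to roughly 65% and 69% in the closed form with VIF 1.5 on the controls. The direction also holds on the overall-rate reading but reverses on the OCA-arm reading, under which the moderate thresholds stand. The size of the shortfall under moderate confounding is therefore not settled until the plan defines the rate and says where the VIF applies.

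The strong-confounding thresholds of 9% and 11% are not challenged. This should be corrected, but it does not affect the validity of the analysis.

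**What to change.** In Section 10.4, Figure 2 and the synopsis:

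1. Define the baseline event rate (control, overall or OCA arm) and state whether the VIF applies to the controls or to the whole variance.
2. Recompute power for the planned SMR-weighted analysis, preferably by simulation with the bootstrap Wald test of Section 10.5. Use 1/d_OCA + VIF/d_control as an approximate check.
3. Report expected OCA events for each scenario.
4. Restate the moderate-confounding thresholds and add an event-rate limit to the mild-confounding statement. Keep 9% and 11% if the recalculation supports them.
5. Beside the 'conservative' remark, note that additional control records do not add OCA events, and show the anticipated LabCorp doubling of both Komodo groups as a separate scenario.

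The cost is one recalculation and revised text. No change in sample size, design, data or analysis is requested.

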10.5. Primary Efficacy Analysis

Standard error estimation will proceed using the nonparametric cluster bootstrap (Davison 2013) as has been suggested for nested trial designs using Cox proportional hazards regression (Gran 2010). The standard error will be used to calculate the 95% CI of the hazard ratio and to conduct statistical hypothesis testing. A total of 1000 bootstrap replicates will be used. Bootstrap sampling will occur at the patient level, rather than the patient index level, thus preserving the covariance structure between patient indices and properly accounting for variance inflation due to the covariance between analytic units. Within each bootstrap replicate, all aspects of estimation will be repeated, including the fitting of the treatment model, the construction of the weights, and the fitting of the weighted Cox proportional hazards model used to estimate the treatment effect. The standard deviation of the bootstrap estimates of the treatment effect will be used as an estimate of the standard error. A Wald test will then be conducted using the bootstrap standard error (Cameron 2008). The test statistic is defined as

 $w = \frac{\hat{\beta}}{s_{\hat{\beta}}}$, where $\hat{\beta}$ is the estimated coefficient of OCA treatment from the fitted Cox model and $s_{\hat{\beta}}$ is the bootstrap standard error of the estimated coefficient. With a sufficient sample size, w will follow a standard normal distribution and the p-value will be computed as the probability of a normal random variable being greater than |w| or less than -|w|. A p-value less than 0.05 will be considered statistically significant.

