The Komodo Health database contains administrative claims from >350 US payers, including commercial (63%); Medicaid (23%); Medicare (10%); dual eligible (<1%); and other (2%). Data are tokenized to allow for patient tracking across payers. Komodo Health claims will be linked through Datavant tokenization to Quest Diagnostics and LabCorp laboratory data, the US National Death Index (NDI), and the Organ Transplant Network (OPTN) transplant registry for additional information and outcome verification. The database contains >100,000 patients with a PBC diagnostic code. The Global PBC registry includes >5,000 patients with PBC recruited from 17 liver centers across 8 countries in Europe and North America. It utilizes the CASTOR trial platform for electronic case report form (eCRF) collection of medical history, clinical events, and laboratory and treatment data.

All patients who meet diagnostic criteria for PBC in each database between 01 Jun 2015 and 31 Dec 2021 and who meet all eligibility criteria will be considered for these studies. The OCA treatment evaluation period will be from 01 Jun 2016 (based on first country approval by Food and Drug Administration on 27 May 2016). The Komodo Health database is US-specific and the Global PBC registry includes the US and multiple other countries with later approval dates. The Sponsor has applied the date of first global approval of 01 Jun 2016 for both studies. The first date of prescription of OCA after inadequate UDCA response (ALP>upper limit of normal [ULN] and/or total bilirubin [TB]>ULN after >270 days of treatment) or UDCA intolerance (discontinued UDCA after <90 days despite ALP>ULN and/or TB>ULN) will be defined as the index date for OCA-treated PBC patients. The dates of evidence of inadequate UDCA response or UDCA intolerance during which OCA is not utilized will be used as an index date for the non–OCA-treated comparator group.

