6.2. Number of Patients

The Komodo Health database contains administrative claims from >350 US payers, tokenized to allow for patient tracking across payers. Komodo Health claims will be linked through Datavant tokenization to Quest Diagnostics and LabCorp laboratory data, the US National Death Index (NDI), and the Organ Transplant Network (OPTN) transplant registry for additional information and outcome verification. The database contains >100,000 patients with a PBC diagnostic code. The Global PBC registry includes >5,000 patients with PBC recruited from 17 liver centers across 8 countries in Europe and North America. It utilizes the CASTOR trial platform for

electronic case report form (eCRF) collection of medical history, clinical events, and laboratory and treatment data.

Komodo Health: In the current Komodo Health database, there are 395 patients who meet criteria for the OCA treatment group:

- Meet PBC claims diagnostic criteria (1 inpatient or 2 outpatient claims)
- Initiate OCA treatment
- Have evidence of UDCA failure

There are 5916 who meet criteria for the control group (OCA-eligible but not currently OCA-treated)

- Meet PBC claims diagnostic criteria (1 inpatient or 2 outpatient claims)
- Have at least 270 days of UDCA use before elevated ALP and/or TB inclusive of up to 4 instances of elevation (inadequate response) or ≤90 days UDCA use before elevated ALP and/or TB (intolerant)
- Have evidence of ALP >ULN and/or TB >ULN

The Komodo Health data have not yet been linked to LabCorp laboratory data. It is anticipated that these numbers will approximately double with the availability of LabCorp data.

Global PBC Registry: The Global PBC registry data are currently being refreshed. A previous analysis identified that 344 patients who had initiated OCA. Among the >5000 patients not treated with OCA, it is anticipated that >2200 will meet criteria for UDCA failure and for inclusion in the control group (Corpechot 2008, Kumagi 2010).

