 - Komodo Health: The Komodo Health data has been linked to the US National Death Index (NDI), and mortality will be recorded as date of death as recorded in the Index
 - Global PBC registry: Death and date of death are reported by the physician via electronic Case Report Form (eCRF) and recorded through the CASTOR trial platform
- Liver transplantation
 - Komodo Health: The Komodo Health data will be linked to the OPTN database to ascertain whether a patient has received a liver transplant and the date of transplant.
 - Global PBC registry: Liver transplant and date of transplant are reported by the physician via eCRF and recorded through the CASTOR trial platform.
- Hospitalization for hepatic decompensation
 - Komodo Health: Hospitalization for hepatic decompensation will be assessed by any hospital admission claim with the following International Classification of Diseases (ICD)-10 codes (in any position) for decompensating events
 - Variceal bleed: ICD-10: I85.01, I85.11, I86.4 and ICD-9: 456.1, 456.21, 456.8
 - Ascites: ICD-10: K70.11, K70.31, K71.51, R18.0, R18.8, J94.8, K65.2 and ICD-9: 567.23, 571.2, 789.51,789.59, 511.8, 567.23

- Hepatic encephalopathy: ICD-10: B15.0, B16.0, B16.2, B17.11, B19.0, B19.11, B19.21, K70.41, K72.11, K72.90, K72.91 and ICD-9: 572.2, 070.0, 070.20, 070.41, 070.6, 070.71; or utilization of lactulose and/or rifaximin.
- Global PBC registry: Hospitalization for hepatic decompensation and date of hospitalization are reported by the physician via eCRF and recorded through the CASTOR trial platform

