12.2. Data De-identification

12.2.1. Global PBC Registry

The data collected at each site are de-identified by removing all identifying data fields (name, address, date of birth, etc.) prior to being sent to the Central Coordinating Site. A unique Global PBC Study Group study number is assigned to each site and each participant within the site and does not utilize identifying information in creating the patient number. Identifiers and their relation to the Global PBC Study Group number are maintained only at the study site and not by the central Data Coordinating Site.

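### Registry study 747-404: neither country nor centre enters the stated weights, Cox model or bootstrap, so the primary estimate may be confounded by them and its standard error may be too small

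*Combined protocol and SAP*

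**What the plan says.** Section 10.5 sets the resampling unit: "Bootstrap sampling will occur at the patient level, rather than the patient index level, thus preserving the covariance structure between patient indices". It adds that this takes proper care of variance inflation from correlated analytic units. The replicates and test follow: "A total of 1000 bootstrap replicates will be used" and "A Wald test will then be conducted using the bootstrap standard error", with significance at p<0.05. One procedure serves both studies.

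Section 6.2 describes the registry as more than 5,000 "patients with PBC recruited from 17 liver centers across 8 countries in Europe and North America". The Synopsis notes that "the Global PBC registry includes the US and multiple other countries with later approval dates", yet one start date, 01 Jun 2016, applies to all. Under Section 8.1, "Hospitalization for hepatic decompensation and date of hospitalization are reported by the physician via eCRF".

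The treatment-model covariates in Section 10.1.1 include neither country nor centre. Section 10.2 adds baseline covariates to the Cox model and names neither. Section 10.8 uses region only as a subgroup factor. In Appendix B, however, Tables 28 and 30 carry a Region/Country row in the treatment model and the balance table, and Table 18B shows country by group before and after weighting. No table shows centre. The site identifier exists, since Section 12.2.1 says "A unique Global PBC Study Group study number is assigned to each site and each participant within the site".

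**The concern.** Keeping a patient's indices together deals with one level of dependence. It does nothing about patients of the same centre or country sharing a propensity to receive OCA and a background event hazard. Uneven OCA use is a fair inference from the approval dates: before local approval, eligible dates in a country would enter almost only as controls. Event hazard could also differ through case mix beyond the listed covariates, or through admission and transplant practice.

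If both vary, the OCA group and the weighted controls come from different mixes of centres. For the actual 17 centres that is a fixed bias of unknown sign. Over the centre effects that might have arisen, it is extra variance that resampling patients does not see. The primary p-value and 95% CI of 747-404 rest directly on this estimate and standard error.

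**Working it through.** **Inputs from the protocol (Sections 6.2, 10.3-10.5).** 344 OCA and 2200 control patients, so 2544 in all and an OCA share a = 344/2544 = 13.5%; event rates 5% to 15%; VIF 1.05, 1.5 or 2.0, for confounding only; "relative hazards ranging from 0.5 to 0.9 with an alpha level of 0.05", two-sided; 17 centres.

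**Assumed inputs (not in the documents).** Between-centre SD of the log hazard (τ) 0 to 0.7; between-centre SD of logit OCA use 0 to 1.5; coefficient of variation of centre size 0.8. To read these:
- The ratio of the 90th to the 10th centile of centre hazard is exp(2 × 1.2816 × τ): 2.2 for τ = 0.3, 3.6 for 0.5 and 6.0 for 0.7.
- Around a median share of 13.5% (logit −1.856), the 10th to 90th centile of centre OCA share is 7.6% to 22.9% for SD 0.5, 4.2% to 36.0% for SD 1.0 and 2.2% to 51.7% for SD 1.5.

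**1. The plan's own figures.** Power = Φ(|ln HR| × √(D·a(1−a)) − 1.96), with D = 2544 × rate / VIF and a(1−a) = 0.1169.
- 8% events, VIF 1.5: D = 135.7; 0.693 × √15.87 = 2.761; power = Φ(0.801) = 78.8%.
- 11% events, VIF 2.0: D = 139.9; 0.693 × √16.36 = 2.804; power = Φ(0.844) = 80.1%.

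These agree with the stated registry thresholds (>8% and >11%). No allowance for centre is included.

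**2. What doubling the error rate would need.** Type I error = 2(1 − Φ(1.96/√F)), with F = 1 + τ² Σ(w1j − w0j)² / V. Here w1j and w0j are centre j's shares of the OCA and control patients, and V = VIF(1/E1 + 1/E0), with E1 and E0 the events per group. A 10% error rate needs F = (1.96/1.645)² = 1.42.

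At 11% events and VIF 1.5, V = 1.5 × (1/37.8 + 1/242) = 0.0458. So τ² Σ(w1j − w0j)² must reach 0.42 × 0.0458 = 0.0192. That means Σ(w1j − w0j)² = 0.077 at τ = 0.5, but 0.21 at τ = 0.3. If OCA shares are equal across centres the sum is zero and the rate stays at 5.0% whatever τ is.

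Averaged over random centre draws at 11% events, as (τ, logit-OCA SD):
- VIF 1.5: (0.3, 1.0) 6.6%; (0.5, 1.0) 9.3%; (0.5, 1.5) 13.1%; (0.7, 1.0) 13.2%.
- VIF 2.0: (0.5, 1.0) 8.1%; (0.5, 1.5) 11.3%.

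**3. Simulation under HR 1.** 1000 datasets per row, SMR-weighted Cox model, 100 patient-level bootstrap replicates with weights refitted. Monte Carlo SE is about 0.7 to 1.1 points.

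| τ | logit-OCA SD | events | type I, planned | type I, centre-stratified |
|---|---|---|---|---|
| 0 | 0 | 11% | 5.2% | 5.7% |
| 0 | 1.0 | 11% | 3.6% | 5.6% |
| 0.3 | 0.5 | 11% | 5.5% | 5.5% |
| 0.3 | 1.0 | 11% | 7.6% | 5.1% |
| 0.5 | 0.5 | 11% | 6.0% | 4.6% |
| 0.5 | 1.0 | 8% | 8.5% | 5.6% |
| 0.5 | 1.0 | 11% | 11.0% | 4.9% |
| 0.5 | 1.0 | 15% | 15.1% | 5.9% |
| 0.5 | 1.5 | 11% | 15.2% | 5.4% |
| 0.7 | 1.0 | 11% | 15.1% | 6.9% |

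In the row (0.5, 1.0, 11%), the mean patient-bootstrap SE is 0.168 and the true SD 0.208, so the true variance is (0.208/0.168)² = 1.53 times the estimated one. Stratifying by centre gives SE 0.183 against SD 0.180. Resampling whole centres without changing the model leaves 9.3% with the normal Wald test and 7.3% with t on 16 df.

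A further weighted simulation gave 5-8% with country strata.

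Limits: one confounder, one index per patient, no covariates in the outcome model, and fewer replicates than planned. How variation divides between and within countries is also an assumption.

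**The case against.** Much of the case on the other side stands.

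- **Event reporting.** A reader might infer that centres report events differently. No document says so. Section 12.4 describes a standardized eCRF, and death and transplant leave little room for reporting style.
- **Resampling.** A reader might also infer that the bootstrap unit is the error. Section 10.5 is right for repeated indices of one patient, and resampling 17 centres does not restore 5%. The problem lies mainly in the covariates and model of Sections 10.1.1 and 10.2.
- **Country.** Approval date is a fact about countries. If the Region/Country row of Tables 28 and 30 reflects the intended treatment model, part of the problem is already handled. But that row conflicts with the Section 10.1.1 list, and country terms would leave any differences between centres within a country.
- **Case mix.** Liver biochemistry, platelets, cirrhosis and portal hypertension are adjusted for, and decompensated patients are excluded. The relevant variation is what remains after that, so the upper assumed values may be too large.
- **Sparse strata.** At 8% events, 344 OCA patients give about 28 events, or about 14 at HR 0.5: 14/17 = 0.8 per centre and 14/8 = 1.8 per country. Weights fitted on pooled data need not balance covariates within strata.

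**Conclusion.** The omission is documented: neither centre nor country is in the stated covariates, Cox model or resampling for 747-404. Its effect is conditional, because both OCA use and event hazard must vary between centres. Type I error is then about 5-8% for modest variation and about 9-15% for larger variation (log-hazard SD 0.5-0.7 with logit-OCA SD 1.0-1.5). It is somewhat lower when the plan's VIF of 1.5 to 2.0 is applied.

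The documents do not support the flat statement that the interval is too narrow or that the false-positive rate doubles. Doubling is attainable within the plan's event-rate range, but only with substantial variation in both quantities. The mechanism is largely confounding by country or centre. The point does not extend to Komodo.

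**What to change.** For 747-404, before outcomes are unblinded under Section 10.1.2:

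1. Stratify the weighted Cox model of Sections 10.2 and 10.5 by country as the default, and by centre where a centre has enough OCA patients and events. State the minimum in advance. Keep the patient-level bootstrap within strata.
2. Reconcile the Section 10.1.1 covariate list with the Region/Country rows of Tables 28 and 30.
3. Check weighted balance within strata as well as overall.
4. Limit the Section 10.5 statement to repeated indices of one patient.

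No new data are needed, since site and country are already held. The cost is nominal power: at HR 0.5 it falls by about 1-8 points with country strata and 5-12 with centre strata when OCA use varies moderately, and by more if it is very uneven. As an example with centre strata, in the (0.5, 1.0, 11%) setting the reported variance rises by (0.183/0.168)² = 1.19. Applied to the plan's own cases, that takes 78.8% to about 72% and 80.1% to about 73%. Part of this is precision the unstratified test did not have: in that setting the estimator's true variance falls by 25%, from 0.208² to 0.180². Komodo needs no change.
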